- 4. FDG-PET/CT and CT with contrast (or MRI) of neck, chest, abdomen, and pelvis FDG-PET/CT and CT with contrast (or MRI, if CT with contrast is contraindicated) will be conducted at Week 6 ± 7 days. Patients continuing on monotherapy will have FDG-PET/CT and CT with contrast conducted at Week 14 and Week 22, ±7 days. Subsequent contrast-enhanced CTs (or MRI, if CT contraindicated) will be performed at Week 34 then every 12 weeks until relapse or disease progression (Week 46, 58, 70, etc.), ±7 days. MRI may be performed only if CT with contrast is contraindicated in the opinion of the Investigator or if frequent CT scans are not allowed according to local IRB/IEC. The same imaging modality used at screening **must** be used throughout the study for each patient.

# 7. Enrollment and Study Procedures

# 7.1. Screening Period

Selected screening procedures are highlighted below. For the additional screening assessments to be performed, please see the Schedule of Events provided in Section 6.1.

#### 7.1.1. Informed Consent

Written informed consent in a language fully comprehensible to the prospective patient and/or designee will be obtained prior to performing any study-related procedures. A copy of the signed informed consent form (ICF) will be provided to the patient and/or designee. The Investigator will retain all original versions of signed ICFs.

After ICF signature, patients who successfully complete all screening assessments and study entry criteria may be enrolled in the study. The period for completing screening assessments is 28 days.

An optional supplemental consent for future use of blood and tissue samples for research purposes (biobanking) may be proposed to patients based on local regulatory requirements (See Section 7.3.4.3).

Rescreening of patients is only allowed once per patient if the patient was not registered as entering the treatment phase before (ie, Cycle 1 Day 1). In this case, a new patient number will be assigned, and the patient will be identified with this number throughout their participation in the study.

#### 7.1.2. Demographic Information

Demographic information will be collected at the Screening visit. Standard demography parameters include age, gender, and race/ethnicity (recorded in accordance with local regulations).

## 7.1.3. Physical Examinations

Physical examinations will be performed as specified in the Schedule of Events (Section 6.1). Documentation of the physical examination will be included in the source documentation at the investigational site. Any changes from the screening physical examination findings that meet the definition of an AE must be recorded on the AE eCRF.

## 7.1.4. Medical History

All lymphoma-related history over the patient's lifetime should be recorded, including:

- Lymphoma diagnosis
- Prior lymphoma therapies and dates
- Responses to prior lymphoma therapies (including stem cell transplantation, radiotherapy, CAR-T cell or other adaptive T-cell therapies, surgery, etc.)
- Whether patient was refractory to their most recent prior therapy

The non-lymphoma-related medical history should include any ongoing medical conditions and symptoms and should also include the toxicity grade.

# 7.1.5. Tumor Specimen

A FFPE tumor block is preferred; if a tissue block is not available, at least 15 unstained slides or freshly cut serial sections (3–5 µm in thickness), preferably with an accompanying block punch will be accepted. A representative tumor specimen or lymph node meeting the following criteria must be available at the time of screening and submitted to the central pathology laboratory within 8 weeks after Cycle 1 Day 1:

- For patients with ENKTL, AITL, PTLD, and HIV-L: Tumor specimen is preferably ≤1 year old. For tumor specimens >1 year old, please consult the Medical Monitor to discuss eligibility.
- For patients with all other lymphoma subtypes: Tumor specimen is preferably ≤6 months old. For tumor specimens >6 months old, please consult the Medical Monitor to discuss eligibility.

The specimen must be representative of the current disease (eg, for patients who have relapsed, the biopsy specimen should have been taken after the most recent relapse).

The process for submitting archived tissue or fresh tissue biopsy as FFPE tissue specimens and procedures for central pathology review is provided in a separate Pathology Manual.

# 7.1.6. Central Review of EBV Status and Verification of Lymphoma Subtype

All enrolled patients will have tumor tissue from a representative biopsy reviewed centrally for confirmation of EBV-positive lymphoma. *In situ* hybridization for EBV encoded RNA (EBER-ISH) and/or immunohistochemistry for LMP-1 will be performed. The central pathology lab slides and local pathology report will be reviewed regarding morphology and ancillary test results to confirm the diagnosis. Appropriate pathology review and/or immunophenotyping will be conducted to confirm the diagnosis.

For clinical trial sites with capability, digital images of slides utilized in local diagnosis, subclassification, and EBV status with controls, will be submitted to the central pathology laboratory.

Patients enrolled based on local pathology results will not be removed from the study if the central pathology lab shows a different result (eg, patient is EBV+ based on local pathology and EBV on central review).

#### 7.1.7. Baseline Disease Assessments

#### 7.1.7.1. FDG-PET/CT and CT with Contrast

Any imaging assessments already completed during the regular work-up of the patient within 28 days prior to Cycle 1 Day 1, including before signing the main study ICF, can be considered as the baseline images if all imaging requirements for the study are met.

An FDG-PET/CT and a diagnostic contrast-enhanced CT (or MRI if a CT with contrast is contraindicated) of the neck, chest, abdomen, and pelvis is required to confirm measurable disease (one target lesion) greater than 1.5 cm in diameter or at least one extranodal lesion greater than 1.0 cm in both long and short diameter. All evaluable or measurable disease must be documented at baseline/screening and re-assessed at each subsequent tumor evaluation.

FDG-PET/CT scans in conjunction with diagnostic contrast-enhanced CT scans will be obtained in this study. Diagnostic contrast-enhanced CT scans obtained as part of a PET/CT scan may be used in lieu of a dedicated CT scan. Patients may have extranodal disease that is inadequately imaged by CT scan. MRI may be preferred in these cases. The same imaging modality used for lymphoma evaluation at screening must be used for all response evaluations throughout the study to ensure consistency across the different time points for each patient.

## 7.1.7.2. Bone Marrow Biopsy

For patients with HL and DLBCL, a baseline bone marrow biopsy is not necessary if the PET/CT demonstrates bone disease.

Patients with HL and DLBCL are only required to have a baseline bone marrow biopsy if clinically indicated (eg, cytopenias are present and the screening PET/CT scan does not indicate bone/bone marrow involvement).

For all other patients, a baseline bone marrow biopsy is required at screening.

If a bone marrow biopsy was performed within 12 weeks prior to Cycle 1 Day 1 and is available, it may be used as the screening biopsy. Bone marrow biopsy samples must be submitted to central pathology within 8 weeks after Cycle 1 Day 1.

The process for submitting tissue to the central pathology laboratory is provided in a separate Laboratory Manual.

### 7.1.8. Eligibility Determination and Patient Registration

Investigative sites will submit patient registration materials for Medical Monitor approval prior to the enrollment of the patient in the trial. Details on this process will be included in the Study Manual.

Once all screening procedures are complete, an eligibility checklist must be completed by the Investigator or designee and provided to the Medical Monitor for review. Eligibility will be reviewed and approved by the Sponsor Chief Medical Officer (CMO) or designee (eg, Medical Monitor) prior to patient enrollment.

#### 7.1.8.1. Screen Failures

Patients who have provided informed consent or assent but are later deemed to be ineligible for enrollment before taking any study medication will be considered screen failures. The eCRF completion requirement for screen failures is outlined in the eCRF Completion Guidelines.

# 7.2. Treatment Period

Patients will be treated with nanatinostat and valganciclovir until discontinuation of study treatment as described in Section 7.2.3.

## 7.2.1. Treatment Cycles

For Cohorts 1, 2, 3b, 4, 5, 6, and 7, patients will receive nanatinostat/valganciclovir (nanatinostat 20 mg orally once daily on Days 1 to 4 per week and valganciclovir 900 mg orally once daily) continuously for 28-day treatment cycles. During treatment Cycle 1, visits will occur on Days 1, 8, 15, and 22. Starting at Cycle 2, visits will occur on Days 1 and 15. Each scheduled clinic visit has an allowable ±3-day window. Visit windows are not applicable to dosing. Should a visit occur during the ± 3-day window, patients will be instructed to continue following the 4 days on, 3 days off dosing cycle for nanatinostat.

For Cohort 3a, the PTCL patients randomized to monotherapy will begin with 6 weeks of nanatinostat monotherapy (20 mg orally once daily on Days 1 to 4 per week) with visits on Days 1, 15, 29, and 43. Each scheduled clinic visit has an allowable ±3-day window. If a patient has stable or progressive disease at the Day 43 visit, the patient will be offered the option to switch to nanatinostat/valganciclovir combination and follow the 28-day treatment cycles as described above. Patients must complete the End of Monotherapy Disease assessment and qualify (labs, no sign of CNS disease progression, ECOG) prior to beginning Cycle 1 Day 1 of the nanatinostat/valganciclovir combination therapy. If a patient has a response (complete or partial response) to nanatinostat monotherapy at the Day 43 visit, the patient will continue monotherapy treatment.

#### 7.2.2. Unscheduled Visit(s)

Unscheduled visits will be recorded in the eCRF. The specific tests and evaluations performed during an unscheduled visit will be determined by the Investigator.

### 7.2.3. Discontinuation of Study Treatment

Patients will continue on study until disease progression, unacceptable toxicity, withdrawal of consent by the patient, patient is lost to follow-up, death, or discontinuation from the study due to any other reason (eg, Sponsor terminates the study).

Patients may voluntarily discontinue from study treatment at any time and for any reason. In this case, the Investigator must make every effort to determine the primary reason for the decision and record this information in the eCRF.

When a patient withdraws consent for participation in the study all data collected up to the point of withdrawal must be maintained in the database and included in subsequent analyses, as appropriate. A patient may withdraw from the interventional portion of the study and yet agree to continued follow-up of associated clinical outcome information in which case this information would be collected and maintained in the clinical trial database.

The Investigator may discontinue study treatment for a given patient if he/she is of the opinion that continuation of therapy would be detrimental to the patient's well-being.

For patients that discontinue treatment without relapse/disease progression, follow the CT scan assessment schedule until disease progression, start of new anti-lymphoma therapy, or end of study (see Table 5).

Patients may be withdrawn from the study if any of the following occur:

- Adverse event
- Progressive disease or relapse
- Lost to follow-up
- Physician decision
- Pregnancy
- Withdrawal of consent
- Death
- Study terminated by Sponsor
- Any protocol deviation where continuing participation in the study would result in a significant risk to the patient's safety

#### 7.2.4. End of Treatment

At the time patients discontinue study treatment, a visit should be scheduled as soon as possible and within 14 days after the last dose of study drug, at which time all assessments listed for the End of Treatment (EOT) visit will be performed. The EOT visit will be recorded in the eCRF with the date and reason for stopping the study treatment. At minimum, all patients who discontinue study treatment, including those who refuse to return for a final visit, will be contacted for safety evaluations during the 28 days following the last dose of study drug(s).

The assessments to be performed at EOT are listed in the Schedule of Events provided in Section 6.1.

## 7.2.5. Safety Follow-up Visit

The Safety Follow-up visit will occur approximately 28 days following the final administration of nanatinostat/valganciclovir. The Safety Follow-up visit has an allowable  $\pm 3$ -day window.

If a patient withdraws consent after the EOT visit but prior to the 28-day safety evaluation, safety data should be collected on the patient up to the date of consent withdrawal.

Adverse events will be assessed (contact by phone is permitted) until 28 days following the last dose of study drug. In addition to AEs, all concomitant medications given to a patient as a result of an AE during this period will be recorded on the Prior and Concomitant medication eCRF page. All new anti-lymphoma therapies given to a patient within 28 days after the last dose of study drug must be recorded in the eCRF.

### 7.2.6. Long-term Follow-up Visits

Patients who discontinue treatment for reasons other than disease progression will start Long-term Follow-up visits every 12 weeks (±7 days) following the EOT visit. Scans performed during the Follow-up period should be performed on the same schedule with the same imaging modality as previously used. Tumor and EBV DNA level assessments will continue as part of the Long-term Follow-up visits until disease progression or start of new anti-lymphoma therapy.

At disease progression/relapse or the start of new anti-lymphoma therapy, patients will be contacted (eg, telephone, e-mail) at least every 6 months (±7 days) following the previous Long-term Follow-up assessment for a description of subsequent anti-lymphoma therapy given, response to subsequent therapies, and survival, unless they withdraw consent.

Long-term Follow-up visits will continue until all patients have either withdrawn consent, died, become lost to follow-up, completed 3 years of follow-up, or the trial is terminated by the Sponsor.

# 7.2.7. Lost to Follow-up

Patients who do not complete scheduled visits and who are unable to be contacted following at least 3 documented attempts (one of which is contact by certified/registered mail) will be considered lost to follow-up.

# 7.3. Assessments During the Treatment Phase

Study treatment will start on Cycle 1 Day 1. Serial assessments of safety and efficacy will be performed as outlined in the Schedule of Events provided in Section 6.1. A central laboratory will be used for the analysis of hematology and chemistry. Clinical decisions and dose modifications during the study can be based on local laboratory results.

## 7.3.1. Efficacy Assessments

#### 7.3.1.1. Baseline Evaluation

The following radiologic assessments are to be performed in the screening period (within 28 days prior to the start of treatment):

- 1. A brain CT or MRI to rule out CNS involvement with lymphoma.
- 2. FDG-PET/CT and diagnostic CT with contrast or MRI from base of skull to mid-thigh (including other known sites of disease) to establish disease status at baseline. A diagnostic contrast enhanced CT scan obtained as part of a PET/CT scan may be used in lieu of dedicated CT scans.

# 7.3.1.2. Tumor Response Assessments

Disease response assessments will be made every 8 weeks until 24 weeks, and then every 12 weeks for the remainder of the study, according to the revised response criteria for malignant lymphoma based on the IWG-NHL guidelines (Cheson 2007). A scan to confirm an unconfirmed PR or unconfirmed  $CR \ge 4$  weeks later may also be performed.

FDG-PET/CT scans in conjunction with diagnostic contrast-enhanced CT scans (or MRI if a CT with contrast is contraindicated) will be obtained in this study at baseline, and for the 8-week and 16-week tumor assessments. Diagnostic contrast enhanced CT scans obtained as part of a PET/CT scan may be used in lieu of dedicated CT scans.

Subsequent evaluations will be by CT with contrast (without PET) or MRI only. Patients with FDG-avid lymphoma at baseline may have an FDG-PET/CT performed to evaluate a possible CR or PR after Week 16 (unless prohibited by local practice) and may use a diagnostic contrast-enhanced CT for follow-up once a complete metabolic response is obtained. FDG-PET/CT scans may also be obtained per investigator discretion (eg, in instances where extranodal disease may be inadequately imaged by contrast-enhanced CT), and responses recorded in the eCRF.

MRI may be substituted only if i) CT is contraindicated as assessed by the Investigator, ii) if frequent CT scanning is not permitted by the local Institutional Review Board (IRB)/Independent Ethics Committee (IEC), or iii) in the case of extranodal disease that is inadequately imaged by CT scan.

At all times during the study, suspected disease progression based on clinical findings must be confirmed by imaging as soon as possible (and before initiating non-protocol specified antilymphoma therapy).

Efficacy will be evaluated in terms of ORR, DOR, PFS, OS, TTP, and TTNLT. ORR will be used to move from Stage 1 to Stage 2. The responses will be assessed by both the Investigator (for management of the patient) and the IRC (for the primary and secondary endpoints).

Investigator-determined response assessments at each assessment time point will be entered onto the appropriate eCRF.

All CT or MRI scan assessments will be determined from date of first dose and will follow the counting of calendar days and not the dosing cycles. It is critical that the same imaging modality used at screening is used throughout the study for each patient. The scans will be performed:

- Every 8 weeks (±1 week) until 24 weeks
- Every 12 weeks ( $\pm 1$  week) for the remainder of the study
- At the EOT visit (unless the previous scan was within 4 weeks of the EOT visit)
- A scan to confirm an unconfirmed PR or unconfirmed CR ≥4 weeks later may also be performed.

If local regulatory authorities mandate less frequent imaging, the minimum frequency must be every 12 weeks.

All patients will be followed for disease progression (ie, PD) or relapse using the schedule described in the Schedule of Events provided in Section 6.1. This includes patients who discontinue the protocol-specified treatments or the study early for any reason without documented evidence of PD or relapse.

Protocol-defined efficacy endpoints except OS and TTNLT will be assessed by an IRC. The IRC review includes central radiology and clinical review. Since the study endpoint is ORR based on PET/CT (first 2 disease response assessments) and thereafter CT with contrast, disease progression will typically be based on CT scans. In limited instances where disease progression is evident only by assessments other than CT, CT scans must still be provided along with the non-CT documentation of disease progression.

The radiologic assessments (FDG-PET/CT, CT with contrast, or MRI) are considered the primary method of response assessment. Any additional assessments – clinical assessments, bone marrow biopsy assessments, etc. are considered confirmatory.

**Repeat bone marrow biopsies** will be performed to confirm CR only for patients with bone marrow involvement reported at baseline.

Patients who relapse or progress will continue to be followed for OS, TTNLT, all subsequent anti-lymphoma therapy, and response, including disease progression/relapse to subsequent lymphoma therapy.

Disease assessment data including actual scan data and radiology reports will be submitted to the Sponsor as it becomes available for evaluation by a central radiology reader.

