- b. Valganciclovir 900 mg orally once daily. Patients with a CrCl 50-59 mL/min at study entry will receive valganciclovir 450 mg orally once daily as per Table 4.

For adolescent patients, see Section 5.2.2 for appropriate dosing recommendations for valganciclovir. Patients who develop disease progression but, in the opinion of the Investigator, would still benefit from continuing study drug may continue treatment with nanatinostat and valganciclovir after agreement with the Sponsor, provided that they are i) asymptomatic from or have no overt signs of disease progression; and ii) have a performance status of 0-1. It is recommended to perform an interval follow-up radiologic disease assessment before the next scheduled time point. Such patients will be recorded as having had a PFS event.

All patients will be monitored at weekly intervals through the first cycle of treatment, and then at 2-week intervals thereafter. Tumor response will be evaluated after every 2 cycles  $\times$  3, and after every 3 cycles thereafter. The responses will be assessed by both the Investigator and an IRC.

Figure 2: Study Design

Note: Patients enrolled with PTCL will be randomized 1:1 to either nanatinostat monotherapy (in Cohort 3a) or nanatinostat plus valganciclovir (in Cohort 3b).

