#### 3.1.2. Treatment Period

Patient eligibility will be confirmed once all screening procedures are completed.

Enrolled patients will receive treatment until disease progression (per Investigator assessment), unacceptable toxicity, withdrawal of consent, Investigator's discretion, death, initiation of new antineoplastic therapy, discontinuation from the study for any reason, or study termination by the Sponsor. Patients receiving nanatinostat monotherapy who have disease progression will be offered the option to receive combination therapy with valganciclovir. All antineoplastic therapies given after the last dose of study drug (and time to next therapy) will be recorded in the electronic case report form (eCRF) (unless the patient withdraws consent or is lost to follow-up). Patients will be followed for survival regardless of treatment discontinuation reason (except if consent is withdrawn or patient is lost to follow-up).

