Valganciclovir dose will be adjusted based on CrCl as described in Section 5.4.1 for patients who develop creatinine elevations/impaired renal function while on study.

- i. **Serum immunoglobulins** Samples will be collected to evaluate serum immunoglobulins including quantitative levels of IgA, IgE, IgG and IgM. Samples will be collected pre-dose and every 3 cycles starting at Cycle 3 Day 1 (Day 1 of Cycles 3, 6, 9, 12, etc.) and at the EOT visit.
- j. **Hepatitis screening** Hepatitis B virus (HBV) surface antigen (Ag), HBV core and surface antibody (Ab), HBV DNA polymerase chain reaction (PCR; only for patients with positive HBV core Ab or surface Ag), hepatitis C virus (HCV) Ab (any patient positive for HCV Ab will be evaluated by qPCR).
- k. **Pregnancy testing** Pregnancy testing is only required for females of childbearing potential. Serum test must be performed during screening. Serum or urine tests are to be performed at the beginning of each cycle, the EOT visit, the 28-day Safety Follow-up visit, and every 12 weeks for 6 months following the last dose of study drug.
- 1. FDG-PET/CT Scans will be performed at Screening, Week 8, Week 16 (±7 days), and subsequently for evaluation of a possible CR or PR. *Diagnostic* contrast-enhanced CT scans obtained as part of a PET/CT scan may be used in lieu of dedicated CT scans.
- m. CT with contrast (or MRI) of neck, chest, abdomen, and pelvis A diagnostic contrast-enhanced CT (or MRI, if CT contraindicated) will be conducted at Screening, Week 8, and Week 16, Week 24 then every 12 weeks until relapse or disease progression (Week 36, 48, 60, etc.), ±7 days. MRI may be performed only if CT with contrast is contraindicated in the opinion of the Investigator or if frequent CT scans are not allowed according to local IRB/IEC. The same imaging modality used at screening must be used for all response evaluations throughout the study to ensure consistency across the different time points for each patient. A scan to confirm an unconfirmed PR or unconfirmed CR ≥4 weeks later may also be performed.

For patients who discontinue due to relapse/progression, the EOT visit FDG-PET/CT and/or CT with contrast is not needed if the last scan was within 4 weeks of the EOT visit.

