4.5.6.2 Handling of Dropouts or Missing Data

Overall response is based on those patients with available data (baseline and post-baseline response assessment). Non-evaluable patients are considered non-responders and will be included in the denominator. Progression-free survival and DOR will be right-censored for patients who meet one of the following conditions: 1) non-protocol systemic anti-cancer treatment started before documentation of disease progression or death, 2) death or disease progression after more than one missed disease assessment visit, or 3) alive and does not have documentation of disease progression before a data analysis cutoff date. These conventions are based on the FDA Guidance for Industry, Clinical Trial Endpoints for the Approval of Cancer Drugs and Biologics (2018) and Clinical Trial Endpoints for the Approval of Non-Small Cell Lung Cancer Drugs and Biologics (2015). The analyses of PFS and DOR will be right-censored according to the conventions described in the table below.

Table 3 Censoring Conventions for Progression-Free Survival, Time to Progression, and Duration of Response

Situation	Date of Progression for Censoring	Outcome
No baseline tumor assessments	Randomization (if applicable) or enrollment	Censored
New anti-cancer therapy started before documentation of PD or death	Date of last disease assessment prior to start of new anti-cancer therapy	Censored*
Death or PD immediately after more than one consecutively missed disease assessment visit	Date of last disease assessment visit without documentation of PD that is before the first missed visit	Censored
Alive and without PD documentation	Date of last disease assessment	Censored
Death or PD between planned disease assessments	Date of death or first disease assessment showing PD, whichever occurs first	Progressed

Situation	Date of Progression for Censoring	Outcome
Death before first disease assessment	Date of death	Progressed

*PFS, TTP, DOR will additionally be analyzed without censoring for hematopoietic stem cell transplant

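### IRC-assessed PFS and TTP have no rule for progression called by the investigator but not by the IRC, although that call in practice ends scanning

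*Protocol*

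**What the plan says.** **Who assesses.** Protocol 7.3.1.2 gives the efficacy endpoints other than OS and TTNLT to the IRC ("Protocol-defined efficacy endpoints except OS and TTNLT will be assessed by an IRC") and divides the roles: "The responses will be assessed by both the Investigator (for management of the patient) and the IRC (for the primary and secondary endpoints").

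**What ends treatment and scanning.** Protocol 3.1.2: "Enrolled patients will receive treatment until disease progression (per Investigator assessment"). The CT footnote to Table 5 (Protocol 6.1) has scans at Weeks 8, 16 and 24, "then every 12 weeks until relapse or disease progression". Patients who stop drug without progression, under 7.2.3, "follow the CT scan assessment schedule until disease progression, start of new anti-lymphoma therapy, or end of study". Section 7.2.6 opens 12-weekly follow-up only to patients who stopped for another reason, with tumor assessments at these "visits until disease progression or start of new anti-lymphoma therapy". After progression, contact is remote and about every 6 months. None of the scan-stopping passages names the assessor.

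**Patients treated on.** Protocol 3.1 (and the synopsis) lets some patients continue drug after progression and adds: "Such patients will be recorded as having had a PFS event". Again no assessor is named.

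**How the SAP handles it.** SAP 3.4.1.2 specifies CRR, TTR, DOR and DOCR per IRC and per investigator, but names no assessor for PFS or TTP. Its PFS definition lists new antineoplastic therapy as an event. Table 3 (SAP 4.5.6.2) censors a patient who starts new therapy before documented progression, one who progresses or dies after more than one consecutive missed assessment, and one who is "Alive and without PD documentation". It has no row for progression on which the two assessors disagree.

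**The concern.** When the investigator calls progression and the IRC does not, the IRC endpoint still needs later scans, but the patient has usually left the scan schedule. On IRC dates the follow-up time then ends in censoring. The patients affected are those a clinician judged to be failing, so the censoring is unlikely to be independent of the outcome, and its effect is to lengthen IRC PFS and TTP.

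There is no control arm for the combination that would share the bias. No investigator-assessed PFS or TTP is planned, so a reader of the report could not see how large it is. These endpoints are descriptive, but SAP 4.5.6.3 links a possible accelerated submission to six months of follow-up for DOR and other secondary endpoints.

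**Working it through.** **Step 1. Trace one patient.** The investigator calls progression on a scheduled scan; the IRC reads the same scan as no progression.

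| What happens next | Table 3 on IRC dates | Other text |
|---|---|---|
| Stops drug, alive, no new therapy | Censored at last assessment | None |
| Stops drug, starts new therapy | Censored at last assessment before it | SAP 3.4.1.2: PFS event |
| Stops drug, dies before more than one missed assessment | PFS event at death | None |
| Stops drug, dies later | Censored, if scans no longer scheduled count as missed (not stated) | None |
| Continues drug | No event unless a later scan is IRC progression | Protocol 3.1: PFS event |

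The same reading can therefore be an event or a censoring, depending on later therapy, on whether drug continues and on which text is followed.

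**Step 2. The plan's own figures.** The documents give no planned event count, power or expected median for PFS, TTP or DOR in this study, so there is no figure to reproduce. The Simon design (10 then 21 patients, stop at 1 or fewer, reject at 5 or more) recomputes to type I error 0.0440 and power 86.15%, against the stated 0.0440 and 86.2%. It concerns ORR and is not touched.

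**Step 3. Illustrative size.** Inputs:
- Median PFS 3.7 months, quoted in Protocol 1.1.2 for relapsed or refractory PTCL; exponential times (assumption).
- Scans at Weeks 8, 16 and 24, then every 12 weeks.
- Share d of events called by the investigator only: not in the documents; assumed 10% to 30%.
- When scanning continues, the IRC calls progression at the next scan (assumption).

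Hazard h = ln 2 / 3.7 = 0.1873 per month. Eight weeks = 8 / 4.348 = 1.840 months. The probability of an event in one 8-week interval is p = 1 − exp(−0.1873 × 1.840) = 0.2915. The last scan before 6 months (26.1 weeks) is Week 24, so three intervals count. The 6-month PFS estimate is:
- investigator progression counted as the event: (1 − p)³ = 35.6%
- discordant patients censored: (1 − (1 − d)p)³
- discordant patients scanned on to IRC progression: (1 − p)³ + d(1 − p)²p

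| d | Censored | Scanned on | Difference |
|---|---|---|---|
| 10% | 40.1% | 37.0% | 3.1 points |
| 20% | 45.1% | 38.5% | 6.6 points |
| 30% | 50.4% | 39.9% | 10.5 points |

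A simulation of 200,000 patients on the same grid gave 40.1%, 44.9% and 50.3% censored, and 36.9%, 38.4% and 39.9% scanned on: differences of 3.2, 6.5 and 10.4 points.

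**Step 4. Medians, as an upper end.** Ignoring the scan grid, censoring a share d of events lowers the hazard to (1 − d)h, and the median becomes 3.7 / (1 − d): 4.1, 4.6 and 5.3 months. For DOR, starting from the 6.5 months in Protocol 1.2.4, 6.5 / (1 − d) gives 7.2, 8.1 and 9.3 months. Both compare with counting every investigator call as a true event.

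**The case against.** **Censoring is inferred.** Table 3 refers to progression documentation without saying whose, and the SAP names no assessor for PFS or TTP. A reader might infer that the plan states that investigator-only progressions are censored. It does not. That outcome follows only when Table 3 is applied to IRC dates, as Protocol 7.3.1.2 implies, and it is not universal: timely deaths stay events, and the SAP's PFS definition makes new therapy an event. What remains is a missing rule and two conflicting texts.

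**Later scans can exist.** An end-of-treatment scan is required unless one was done within 4 weeks, clinically suspected progression must be imaged, and patients treated on have an interval scan recommended. Protocol 7.3.1.2 also follows patients who stop without documented progression. This narrows the problem. However, the end-of-treatment visit falls within 14 days of the last dose, so the scan that prompted the call will often satisfy the 4-week waiver. Imaging a suspicion also does not make two readers agree. That a site applies the stopping rule to its own call is an inference, though a natural one, since nothing in either document makes sites wait for an IRC reading. The IRC charter is not available here.

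**The SAP supersedes the protocol's analysis plan.** SAP Section 1 says so, and the SAP does not repeat the sentence about patients treated on. But that sentence stands in the protocol's design text, outside its statistics section, and SAP 4.8 does not list it as changed. Its status is unclear.

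**DOR is covered.** Largely so: an investigator analysis is planned. It uses investigator-defined responses, so it does not isolate disagreement about progression among IRC responders.

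**The size is assumed.** This stands. The share d is applied to all events, including deaths, which cannot be investigator-only. Against counting every investigator call as an event, the 6-month gap is 4.6, 9.5 and 14.9 points (unrounded inputs); about 30% of it is a difference between two endpoints, not bias. Disagreement in the other direction, with the IRC earlier than the investigator, is not modeled.

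**Conclusion.** The concern holds as a gap in specification with a likely direction of bias. PFS and TTP are IRC endpoints, scheduled scanning in practice stops at the investigator's call for patients who stop drug, and the SAP does not say what happens when the IRC disagrees. Followed on IRC dates, Table 3 would censor most of these patients, and no planned analysis of PFS or TTP would show the effect. IRC DOR is exposed to the same mechanism but has a planned investigator counterpart.

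Under exponential times, a 3.7-month median and an assumed 10% to 30% discordance, 6-month PFS would be about 3 to 10 points too high relative to continued scanning to IRC progression. The medians of 4.1 to 5.3 months are an upper-end illustration; a reader might take them as a measured inflation, which the documents cannot support because they give no discordance rate. Nor do the documents support extending the point to the primary ORR or the Simon decisions, which do not depend on these censoring rules.

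**What to change.** 1. In SAP 3.4.1.2, define PFS and TTP per IRC and per investigator, as is already done for DOR.
2. Add to SAP Table 3 a sensitivity analysis for PFS, TTP and DOR in which investigator progression without IRC progression counts as an event on the investigator's date. Add a table cross-classifying investigator and IRC progression calls.
3. Reconcile the sentence on patients treated on (Protocol synopsis and 3.1) with the IRC endpoint, for example by stating that the recorded PFS event is per investigator. Reconcile the SAP 3.4.1.2 PFS definition with Table 3 on new anti-cancer therapy.

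The cost is SAP and protocol wording and a few extra tables. Investigator assessments at each time point are already entered in the eCRF, so no extra scans or patients are needed and treatment is unchanged. The drawback for the sponsor is a possibly less favorable figure beside the IRC one.
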